### 8.2. Recruitment:

We will approach providers using the following methods:

**Primary care team meetings:** We will introduce the study at primary care team meetings and grand rounds.

At the end of the presentation, we will ask providers to complete an enrollment sheet indicating their willingness, or not, to participate and a short demographic survey. Providers will either return the enrollment forms to trial staff after the meeting or mail it to us after the meeting. For providers who do not indicate their willingness, we will send an email inviting them to participate (see next section).

**Email:** We will invite providers via email if they do not return an enrollment sheet after a team meeting or if they are hired after the intervention launches. The email will contain an overview of the study, and a link to a detailed study description and the demographic survey, as well study contact information. The email will ask providers to review the material and reply if they wish to be excluded. The email explains that we will consider them enrolled in the study if they do not respond within one week (default opt-in), and that they could withdraw at any time.

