### **9.3. Additional eligibility criteria.**

- A patient may have more than one index discharge if the 180-day outcomes period for the prior index discharge is completed and was with a provider in the control group. Once a patient has a discharge with a provider in the intervention group, they cannot have additional index discharges. We will include each patient's first discharge only in primary analyses.
- We will exclude patients for whom we would not be able to provide recommendations including those discharged to a domiciliary unit, a nursing home, respite care, or to hospice.
- We considered patients discharged and readmitted within 12 hours to have a continuous hospital admission.

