### **10.1. Recommendations for COPD guideline care:**

**Each week**, for patients with a new index discharge and under the care of a provider in the intervention group, we will perform the following:

**Chart abstraction:** A study coordinator will cut and paste pertinent sections of the EHR into an abstraction template ([Appendix 1](#)). These abstractions will include notations from emergency care, discharge summaries, primary care, pulmonary/sleep, social work, advanced directives, post-discharge telephone calls, and procedures and imaging studies.

**Clinical review:** The intervention team, consisting of pulmonary, primary care, and pharmacy providers, and study coordinators will convene to prepare recommendations for each patient with an abstraction as follows:

- Clinical lead:
  - A pulmonologist or PCP team member will be designated to lead the review each week
  - Reviews the abstractions, and/or EHR as needed, to draft a recommendations checklist ([Appendix 2](#)). The checklist will include:
    - Recommendations for diagnostic testing, medications, therapies/referrals, and/or follow-up, addressing any gaps in contemporary COPD guideline recommended care and related co-morbidities.
    - Draft of the recommendations note that will be placed into the EHR for the PCP's review.
- Review meeting:
  - Moderator: clinical lead.
  - Attendees: a clinical team consisting of at least one pulmonologist and one PCP, with input by the pharmacist as needed, and coordinators.
  - Review: the clinical team will discuss each patient's history, consulting the abstraction and EHR as needed, and identify any gaps in guideline COPD/comorbidity care.
- Recommendations:
  - Final recommendations: modify draft recommendations checklist as appropriate per team review
  - Language/content: ensure that notations will be acceptable to primary care providers. For example, smoking cessation counseling:

- Do not recommend if there have been notations reflecting previous discussions.
- Do offer recommendations such as addition of pharmacotherapy for smoking cessation if none has been previously offered.
- No recommendations: if a patient is receiving all guideline care, reinforce the excellent work.

**Entering recommendations and/or orders into EHR:** We will provide recommendations to the PCP timed to coincide with the patient's post-discharge clinic follow-up (usually within two weeks of discharge) as follows:

- EHR notation:

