## 12.1. Primary outcome measures

**Hospital readmission and mortality:** assess 180 days after the index discharge with a composite measure of any hospital readmission or death.

**COPD specific health status:** measured with the *Clinical COPD Questionnaire (CCQ)*, which consists of 10 items that encompass three domains (symptoms, functional state, mental state). Scores range from 0-to-6 with higher scores indicating better health. The minimally important difference (MID) is 0.39 with a standard error of 0.21.

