## 13. Analytic Approach

---

Our modified stepped wedge design, through its randomized intervention allocation, offers several advantages to interval validity compared to observational approaches. However, our clustered design also requires additional analytic evaluation compared to a simple two-arm randomized trial. The primary outcome measure is COPD hospital readmission/mortality within 180 days as assessed through the CDW. Time zero for intervention patients is the start of the period when the provider cluster is randomized to receive the intervention. Time zero for control patients is the start of each 30-day period (wedge) while the provider cluster remained unexposed to the intervention. Provider clusters randomized to receive the intervention at later time periods will accrue fewer patients than clusters randomized to earlier periods. We will present the analysis for hospital readmission as the example for the analytic approach that would also apply for our secondary outcome measures.

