### 13.1. Models

We will use mixed-effects linear regression or logistic regression as appropriate for the outcome of interest (180-day readmission or death, CCQ Total Score, VR-12 PCS) with clustering by provider:  $g(E(y_i|\mathbf{X}_i, \alpha_{j[i]}) = \mathbf{X}_i\beta + \alpha_{j[i]}$ , where  $y_i$  is the outcome for patient  $i$  and  $\alpha_{j[i]}$  is a random effect for provider  $j$  seen by patient  $i$  such that, across providers, the  $\alpha_{j[i]}$ 's are assumed independently and identically distributed (i.i.d.)  $Normal(0, \sigma_\alpha^2)$ .  $\beta$  is a  $7 \times 1$  vector of fixed effects regression coefficients, and  $\mathbf{X}_i$  is a  $1 \times 7$  vector containing the following fixed effects terms for patient  $i$ : a constant term (identical across patients), an indicator for patient  $i$ 's receipt of the intervention ( $X_i^{Intervention} = 1$  if patient  $i$  received the intervention,  $X_i^{Intervention} = 0$  otherwise), three time-based restricted cubic spline terms for patient  $i$ , the number of days in the past year that patient  $i$  was exposed to systemic corticosteroids, and the number of COPD exacerbations not requiring admission experienced by patient  $i$  in the past year. The logistic link function was used for the 180-day readmission or death GLMM such that  $E(y_i|\mathbf{X}_i, \alpha_{j[i]}) = \pi_i = (e^{\mathbf{X}_i\beta + \alpha_{j[i]}})/(1 + e^{\mathbf{X}_i\beta + \alpha_{j[i]}})$ . The identity link function was used for the CCQ Total Score and VR-12 PCS GLMMs such that  $E(y_i|\mathbf{X}_i, \alpha_{j[i]}) = \mu_i = \mathbf{X}_i\beta + \alpha_{j[i]}$ .

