### 13.2. Sampling and non-response bias and missing data

We will perform an intention-to-treat analysis. The analysis will include all patients in the groups and time period which they were randomly assigned to begin receiving treatment, regardless of their adherence with the treatment and/or subsequent participation. An adjusted odds ratio will be estimated to compare control and intervention group odds of 180-day readmission or death, and adjustment mean differences will be estimated to compare control and intervention group means for CCQ Total Score and VR-12 PCS. In the event of missing outcome data, the primary analysis of the respective outcome will be based on outcome data imputed under a multiple imputation using chained equations procedure, with inference from 70 models of imputed data combined using Rubin's Rules. Sensitivity complete-case analyses will be performed for outcomes with missing values to assess whether direction of association or statistical significance is impacted by a change in missing data approach.

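### Section 13.1 codes the treatment indicator by patient-level receipt, which is settled after the 180-day clock starts, whereas Section 13.2 requires analysis by randomised group and period

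*Combined protocol and SAP*

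**What the plan says.** All references are to the combined protocol and SAP.

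- **Section 13.1 (Models)** gives each patient an indicator for "receipt of the intervention": 1 if the patient received it, 0 otherwise. It is the only treatment term in the model and the only definition from which an analyst could program it.
- **Section 13.2** states "We will perform an intention-to-treat analysis" and continues: "The analysis will include all patients in the groups and time period which they were randomly assigned to begin receiving treatment". Adherence and later participation are not to matter.
- **Section 13** goes by the cluster's schedule: "Time zero for intervention patients is the start of the period when the provider cluster is randomized to receive the intervention". Control patients are tied in the same way to periods in which their cluster had not yet crossed over.
- **Section 13.3** defines X in the power model by cluster and time interval.
- **Section 9.3** also goes by the provider's group: "Once a patient has a discharge with a provider in the intervention group, they cannot have additional index discharges".
- **Section 12.1** starts the outcome at discharge: "assess 180 days after the index discharge with a composite measure of any hospital readmission or death".
- **Section 10.1** describes a weekly review after discharge. Recommendations reach the primary care provider around the first clinic visit, normally inside two weeks.

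**The concern.** The two codings differ for any patient of an intervention-group provider to whom no recommendations are sent. Whether a patient is sent recommendations becomes known only some days into the 180-day window, so a receipt indicator uses information from after baseline.

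Consider a patient discharged after the cluster's crossover who dies or is readmitted on day 5 and is then sent nothing. Section 13.2 counts an intervention patient with an event. Section 13.1, taken literally, counts a control patient with an event. Early events of this kind can only leave the intervention group and join the control group. This is immortal-time bias, and it makes the intervention look better even if it does nothing. The primary odds ratio is what is at stake.

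**Working it through.** **1. The plan's own figure.** Section 13.3 gives power 0.874 for a fall from 0.40 to 0.36. Take I = 30 clusters, T = 31 (period 0 plus 30 steps), N = 15, coefficient of variation 0.1 and two-sided alpha 0.05. Then:
- σ² = 0.38 × 0.62 / 15 = 0.01571; τ² = (0.1 × 0.40)² = 0.0016.
- U = 465, W = V = 9,455; IU − W = 4,495; U² + ITU − TW − IV = 71,920.
- Var = 30 × 0.01571 × (0.01571 + 31 × 0.0016) / (4,495 × 0.01571 + 71,920 × 0.0016) = 0.000166, so SE = 0.01287.
- Power = Φ(0.04/0.01287 − 1.96) = 0.874.

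The figure reproduces using cluster-period coding. Aligning 13.1 with that coding leaves it unchanged.

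**2. Inputs for the illustration.**
- From the documents: 180-day risk 0.40 and planned risk 0.36 (Section 13.3); about 10 discharges per wedge (Section 15); delivery usually within two weeks (Section 10.1).
- Planned odds ratio: (0.36/0.64)/(0.40/0.60) = 0.844, a difference of −4.0 points.
- Discharges: 31 periods × 10 = 310. The intervention share of cluster-periods is 465/930 = 1/2, so about 155.
- Assumed: no true effect; constant hazard; equal accrual; delivery at day L = 7 or 14. A share u of patients with an event before day L is never sent recommendations. The documents give no value for u; 25% to 100% is shown.

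**3. Share recoded.** f = u × (1 − 0.6^(L/180)). The event risk before delivery is 0.0197 at day 7 and 0.0390 at day 14.

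**4. Crude effect, equal groups.** The risk is (0.40 − f)/(1 − f) in those coded 1 and (0.40 + f)/(1 + f) in those coded 0.
- f = 0.25 × 0.0197 = 0.0049: 0.3970 against 0.4029, or −0.6 points.
- f = 0.0390: 0.3757 against 0.4225, or −4.7 points.

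**5. With period in the model.** This is a logistic regression on expected counts for 30 clusters over periods 0 to 30, scaled to 310 discharges. It contains the receipt indicator and a three-term restricted cubic spline; a 3-knot, two-term spline gives the same values. It has no random effect or other covariates. Two-sided rejection is Φ(−1.96 − z) + Φ(−1.96 + z), with z = log OR / SE and SE between 0.284 and 0.289.

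| Delivery | u | Patients recoded (155 × f) | Odds ratio | Risk difference (points) | Rejection |
|---|---|---|---|---|---|
| any | 0% | 0 | 1.00 | 0 | 5.0% |
| day 7 | 25% | 0.8 | 0.96 | −0.9 | 5.2% |
| day 7 | 100% | 3.0 | 0.86 | −3.6 | 8.2% |
| day 14 | 25% | 1.5 | 0.93 | −1.8 | 5.8% |
| day 14 | 50% | 3.0 | 0.86 | −3.6 | 8.1% |
| day 14 | 100% | 6.0 | 0.75 | −7.0 | 17.6% |

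The adjusted shift exceeds the crude one because recoded patients fall mostly in late periods, where few true controls remain.

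**6. Where it meets the planned effect.** At day 14 the odds ratio falls to about 0.844 when u is roughly 58%, or 155 × 0.58 × 0.0390 = 3.5 patients. At day 7 it is not reached even with u = 100%.

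**7. Sensitivity to the hazard.** In the crude two-group calculation, suppose 5%, 10% or 20% of all events fall before receipt. The odds ratio is 0.905, 0.818 or 0.667 if all of these block delivery, and 0.951, 0.905 or 0.818 if half do.

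**The case against.** The strongest reply is that 13.1 sets no rival rule. Elsewhere the documents use the verb for assignment: Section 13.3 has a cluster receiving the intervention at a time, and Section 13 has clusters randomised to receive it. No section defines a patient-level receipt event such as a note posted or an order signed. Section 13.2 states the as-randomised principle and says that the odds ratio compares the control and intervention groups. On this view "receipt of the intervention" is shorthand for discharge under an intervention-group provider. That may well be the intent, and a reader who infers that the trial planned an as-treated primary analysis goes further than the documents allow. Even so, the text of 13.1 is patient-level and does not say what 13.2 says.

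The second reply is that the divergent patients are inferred. Section 10.1 applies the weekly process to all new index discharges under intervention-group providers and makes no exception for death or readmission. Even a patient with no care gaps gets a note. Section 8.2 tells providers that "they could withdraw at any time", but a withdrawal is not triggered by a patient's early event and would not by itself produce this bias. All of this stands, and it is why u is an assumption.

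The third reply concerns size. A reader might infer that the bias matches or exceeds the planned effect. Most of the range in the table does not support that; only its upper corner does. The lower bound of 25% is no better supported than the upper, and constant hazard is also assumed, while Section 4 describes relapse as peaking within 8 to 12 weeks. These points stand too.

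**Conclusion.** The inconsistency is real and should be corrected. Section 13.1, coded as written, conditions on a post-discharge event, contrary to Section 13.2 and to the coding in Section 13.3. Any resulting bias from early events favours the intervention.

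Its size cannot be fixed from the documents. It is zero if every intervention-group patient is sent recommendations. Under the stated assumptions the null odds ratio runs from 0.96 (day 7, 25% not sent) to 0.75 (day 14, 100% not sent), with rejection from 5.2% to 17.6% against a nominal 5%. The planned 0.844 is reached only with day-14 delivery and about 58% or more not sent. The illustration leaves out the provider random effect and the two clinical covariates.

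The documents do not establish that the analysis was meant to be by receipt, that early events stop delivery, or that a bias as large as the planned effect is to be expected. The 180-day anchor at discharge is clear from Section 12.1 and is not in question.

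**What to change.** - **Section 13.1:** define the indicator as 1 if, on the date of patient i's index discharge, the randomised crossover period of the provider's assigned cluster had started, and 0 otherwise, whether or not recommendations were sent.
- **Section 13:** state that the time-zero sentences classify cluster-periods as control or intervention, and that outcome follow-up starts at the index discharge in both groups, as in Section 12.1.
- **Reporting:** give the number of intervention-group patients not sent recommendations. This shows directly whether the two codings would have differed.
- **Any analysis by receipt**, if one is done, should be labelled supplementary.

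The cost is one definition and one clarifying statement. Cluster assignments, crossover dates and discharge dates are already part of the trial's data. The sample size and stated power do not change.

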### 12.4. Baseline Characteristics:

- Sociodemographic: patient and provider characteristics at enrollment using a combination of CDW and self-report.

We will use CDW to identify/calculate the following:

- COPD and medications: results from patients' most recent pulmonary function tests and pulmonary medication prescriptions over the past 12 months.
- Days exposed to steroid: number of days a patient was prescribed an oral corticosteroid in the year prior to index admission.
- COPD exacerbations not requiring hospitalization: number of outpatient exacerbations over the year prior to the index discharge, defined by a primary outpatient ICD-9 or ICD-10 diagnosis associated with a clinical event and prescription for an antibiotic and systemic corticosteroid within 2 days of the diagnosis.

- Comorbidities and health status indicators: collected information on common comorbidities that comprised the health inventory checklist used in previous intervention studies for the year prior to and through the index admission:
  - diagnoses for COPD and common co-morbidities such as diabetes, liver disease, chronic heart failure, vascular disease, and the like to include diagnoses that comprise the Charlson comorbidity index
  - number of all-cause admissions
  - number of inpatient COPD exacerbations
  - number of COPD outpatient exacerbation
  - length of admission
  - Intensive care unit hours during index admission

Table 1. Summary and timing of data elements.

	Data element	Source	Timing
Primary Outcomes	Hospital readmission	Record review, CDW, patient self-report, CMS (on early participants)	180 days post index discharge
	Mortality	Record review, CDW	
	Clinical COPD Questionnaire	Patient self-report	6 weeks post index discharge
Secondary Outcomes and other measures	VR-12		
	Patient satisfaction / smoking status		
	Care recommendations	EHR chart review	180 days post index discharge
	Quality of COPD care	EHR chart review, CDW, patient self-report	
	Provider satisfaction	Provider self-report survey	2 weeks after receiving recommendations for intervention discharge
		Interview	After receiving recommendations for intervention patient
Key Characteristics	Patient sociodemographic	Patient self-report and CDW	6-weeks post index discharge
	Provider sociodemographic	Provider self-report and CDW	Enrollment
	Comorbid diagnoses	CDW	1 year prior to index discharge
	All cause hospital admissions		
	Inpatient and outpatient exacerbations		

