### 13.3. Sample size and study power

For the sample size calculation, let the design have  $I$  clusters,  $T$  time points, and  $N$  individuals sampled per cluster per time interval. Assume the model,  $Y_{ij} = \mu + \alpha_i + \beta_j + X_{ij}\theta + e_{ij}$ , where  $\alpha_i$  is a random effect for cluster  $i$  such that  $\alpha_i \sim N(0, \tau^2)$ ,  $\beta_j$  is a fixed effect corresponding to time interval  $j$ ,  $X_{ij}$  is an indicator of the treatment mode in cluster  $i$  at time  $j$  (1=intervention; 0=control),  $\theta$  is treatment effect and  $e_{ij} = \sum_k e_{ij}/N$  are independent and identically distributed  $N(0, \sigma^2)$  and  $\sigma^2_e/N$ . Let  $Y_{ij}$  be the mean for cluster  $i$  at time  $j$ .

Assume testing the hypothesis  $H_0: \theta = 0$  versus  $H_A: \theta = \theta_A$ , where  $\theta_A$  is the treatment effect size. The

approximate power for conducting a two-tailed test of size alpha is  $power = \Phi\left(\left(\theta_A/\sqrt{Var(\hat{\theta})}\right) - Z_{1-\alpha/2}\right)$

where  $\Phi$  is the cumulative standard normal distribution function,  $Z_{1-\alpha/2}$  is the  $(1 - \alpha/2)$ th quantile of the standard normal distribution function and  $\hat{\theta}$  is the estimated treatment effect size. Let  $X_{ij} = 0$  if cluster  $i$  receives the control at time  $j$  and let  $X_{ij} = 1$  if cluster  $i$  receives the intervention at time  $j$ . Thus with this matrix  $\mathbf{X}$  and assuming equal  $N$  per cluster per time interval, then assume  $Var(\hat{\theta}) = [I\sigma^2(\sigma^2 + T\tau^2)]/[(IU - W)\sigma^2 + (U^2 + ITU - TW - IV)\tau^2]$  where  $U = \sum_{ij} X_{ij}$ ,  $W = \sum_j (\sum_i X_{ij})^2$  and  $V = \sum_i (\sum_j X_{ij})^2$ . This variance equation is used in the power calculation. We have approached the power estimates conservatively allowing for a lower proportion of subjects who may experience hospital readmissions, allowing for regression to the mean.

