We assume 30 unidirectional movements from control to intervention among 30 clusters (clinics) and 15 individuals sampled per cluster per time interval. We assume a significance level of alpha = 0.05. We assume baseline hospital readmission of 0.40 with a 10% relative reduction to 0.36, baseline CCQ of 0.40 with a 10% relative reduction to 0.36, and baseline SF-12 of 0.35 with an 11% relative increase to 0.39. We assume each outcome to have a coefficient of variation equal to 0.1. Under these assumptions, our power is estimated for hospital readmission, CCQ, and SF-12 analyses to be 0.874, 0.874, and 0.889, respectively.

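### The outcome models leave out the prior-year admission count the trial already collects; adding it is a small, nearly cost-free improvement, not the correction of an error

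*Combined protocol and SAP*

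**What the plan says.** Section 13.1 lists seven fixed effects: a constant, the intervention indicator, three restricted cubic spline terms for time, days of systemic corticosteroid exposure in the past year, and "the number of COPD exacerbations not requiring admission experienced by patient" i over the same year. The same vector serves 180-day readmission or death (logistic), CCQ total score and VR-12 PCS (both linear).

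Section 12.4 lists "number of all-cause admissions" and "number of inpatient COPD exacerbations" among the baseline items, with a window covering the prior year through the index admission. Table 1 repeats both items. Section 12.1 defines the first primary outcome as any hospital readmission or death by 180 days. Section 13.2 reports the treatment effect on that outcome as an adjusted odds ratio.

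No reason is given for the choice of covariates. Section 15 (entry of 12/28/18) does record a wish to save degrees of freedom, but in relation to the time terms.

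**The concern.** The model keeps the milder history (exacerbations managed without admission) and leaves out the history of the kind of event being predicted. A patient's past admissions are a natural candidate predictor of the next one. The trial has few patients: Section 15 reports about 10 discharges per wedge. Patients under control and under intervention could therefore differ by chance in how often they had been admitted before. A pre-specified term would remove that imbalance from the estimate and might add some power. CCQ and VR-12 are collected only about six weeks after discharge, so neither has a baseline value to adjust for. Baseline history and characteristics must do that work.

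**Working it through.** **1. The plan's own figure.** Inputs from Section 13.3: "30 unidirectional movements from control to intervention among 30 clusters (clinics) and 15 individuals sampled per cluster per time interval"; "We assume baseline hospital readmission of 0.40 with a 10% relative reduction to 0.36"; "We assume each outcome to have a coefficient of variation equal to 0.1"; "We assume a significance level of alpha = 0.05", two-tailed.

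- I = 30 and T = 31 (period 0 plus 30 steps), so U = 465, W = 9,455 and V = 9,455.
- τ = 0.1 × 0.40 = 0.04, so τ² = 0.0016.
- σ² = 0.38 × 0.62 / 15 = 0.01571, using the mean of the two proportions.
- IU − W = 13,950 − 9,455 = 4,495.
- U² + ITU − TW − IV = 216,225 + 432,450 − 293,105 − 283,650 = 71,920.
- Var = 30 × 0.01571 × (0.01571 + 31 × 0.0016) / (4,495 × 0.01571 + 71,920 × 0.0016) = 0.0001657, so SE = 0.0129.
- Power = Φ(0.04 / 0.0129 − 1.96) = 0.874, as stated.

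No covariate enters this calculation, so the omission cannot affect it.

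**2. Can the model afford the term?** About 10 discharges × 31 periods = 310. At the planning rate of 0.40 that is 0.40 × 310 = 124 events. Eight coefficients give 124 / 8 = 15.5 events each.

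**3. What the term might gain in the logistic model.** The documents give no prognostic strength, so odds ratios per prior admission of 1.2, 1.35 and 1.5 are assumed. Simulation: 3,000 trials of 310 patients, with an existing prognostic covariate (assumed odds ratio 1.3 per SD) already in the model, correlated 0, 0.3 or 0.5 with prior admissions, and an assumed treatment log odds ratio of −0.8. Gain in effective sample size = (mean z with the term / mean z without it)² − 1.

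| Odds ratio per prior admission | Gain | Power at correlation 0.5 |
|---|---|---|
| 1.2 | 0.7–1.1% | 0.708 → 0.710 |
| 1.35 | 2.9–3.8% | 0.699 → 0.713 |
| 1.5 | 5.3–5.9% | 0.657 → 0.682 |

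The Monte Carlo SE of one power figure is about √(0.7 × 0.3 / 3,000) = 0.008. With no existing covariate in the simulation, the gains are 1.6%, 3.5% and 6.9%, so ignoring the overlap overstates them slightly.

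**4. Where that gain comes from.** The SE of the log odds ratio does not fall. It rises from 0.322 to 0.326 in the weakest case and from 0.324 to 0.335 in the strongest. The gain arises because the conditional effect moves further from 1 and chance imbalance is removed. With no treatment effect, adding the term moved the log odds ratio by an SD of 0.038 (odds ratio 1.2) to 0.077 (odds ratio 1.5). The planned log odds ratio is ln[(0.36/0.64)/(0.40/0.60)] = −0.170, so these shifts are 22% to 45% of it. Type I error did not change (0.057 and 0.057; 0.053 and 0.054).

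**5. At the planned effect.** With 310 patients and 0.40 falling to 0.36, simulated power is 0.08 to 0.09 with or without the term. The Section 13.3 formula agrees: at N = 10/30 = 0.33 per cluster-period, power is 0.083, and 0.090 if prior admissions explain as much as 15% of the variance.

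**6. Linear outcomes.** In the CCQ and VR-12 models residual variance falls directly, and the gain is 1/(1 − R²) − 1. An additional R² of 5% gives 5.3%, and 10% gives 11.1%. Both R² values are assumptions; nothing in the documents shows that prior admissions predict either score.

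**The case against.** The strongest reply is that nothing here is wrong. The covariates are stated explicitly, the stated power does not depend on them, and chance imbalance under randomisation is not bias: the standard error already allows for it. Section 12.4 offers other candidates, including lung function, Charlson comorbidities, length of stay and ICU hours, and the documents do not single out prior admissions as the best. Steroid days may already carry part of the same information. The larger precision problem is the gap between 15 individuals per cluster per interval (30 × 31 × 15 = 13,950) and about 310 patients, which no covariate can close.

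All of this stands, and it limits the point to a minor one. It does not remove it. The gain survives in simulation when a correlated covariate is already in the model. Protection from chance imbalance is worth having when a typical shift is 22% to 45% of the planned effect, although it is small beside an SE of about 0.3.

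Three stronger readings are tempting. A reader might infer that adjustment gives free precision; on the plan's odds-ratio scale the SE rises, and one coefficient is spent. A reader might take the gains of up to 2.5 power points as what this trial would see; they assume a log odds ratio of −0.8, not the planned −0.170. A reader might suppose the count is complete; Section 15 says Medicare data were not used, and no section claims completeness.

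**Conclusion.** The point holds as a missed, nearly cost-free improvement of minor weight. The model omits a baseline count that is already collected and is of the same kind as the first primary outcome, with no reason given. The likely benefit is about 1% to 6% in effective sample size for readmission or death. That rests on assumed odds ratios of 1.2 to 1.5 per prior admission, one existing covariate of assumed strength, about 310 patients and a treatment effect larger than planned. For CCQ and VR-12 PCS there is a benefit only if the count predicts those scores.

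The documents do not support calling the present analysis biased or the stated power wrong because of this omission. Nor do they support the view that the term would repair the low power at about 310 patients.

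**What to change.** In Section 13.1, add one pre-specified fixed effect to the models for 180-day readmission or death, CCQ and VR-12 PCS: the number of VA-recorded all-cause admissions in the year before the index admission, capped (for example at 5). Keep the current covariates and make the vector 8 × 1. State that the index stay is excluded, because the window in Section 12.4 runs through the index admission. Include the term in the multiple imputation model of Section 13.2. The documents do not say whether outcomes had been examined; if they had, report the adjusted model as a labelled sensitivity analysis.

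The cost is one degree of freedom and a few lines of text, with no new data collection. The remaining weakness is that admissions outside the VA are not captured.
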